This analysis is focused on the secondary and exploratory patient outcomes for this study, using administrative and survey data for the WA survey sample. Surveys will be conducted at approximately 6 weeks (baseline), 6 months, and 12 months after injury. Our estimates are rough and will be updated as survey enrollment proceeds. However, we anticipate that roughly 3,120 workers in WA will complete baseline surveys, that roughly 1,700 will completed 12-month outcome surveys, and that approximately half of those interviewed will have an attending provider affiliated with COHE.

This analysis will test Hypothesis 2A (stated above) with respect to patient outcomes, using parallel analyses to those described in Analysis Topic H. Most secondary and exploratory patient outcomes will be based on survey data, but several will be based on WC data (see Tables 2 and 3). The only adjustments to Analysis Topic H are that models will include only the WA survey sample, and the binary primary predictor and propensity score calculations will be based on COHE status rather than on state jurisdiction (1 for COHE, 0 for non-COHE).

Additional Information Relevant to Quantitative Analyses for Aims 1, 2, and 2A

Subgroups of Interest

Planned subgroup analyses are listed under the relevant analysis topics above. Because all subgroup analysis will be exploratory, non-exhaustive examples of potential subgroups have been specified. New subgroups of interest may be identified via exploratory data analysis and/or proposed ad hoc by the principal investigator, co-investigators, or stakeholders. The total number of subgroup analyses—and all subgroups and outcomes analyzed—will be reported, along with subgroup definitions and procedures used. If indicated, multiple comparisons will be accounted for using p-value adjustment.

Operational Definitions for Eligibility Criteria

These definitions will need to be aligned as much as possible across the two states. The following operational definitions are based on our history of working with WA WC data. They may need to be modified after preliminary OH WC data are available for inspection.

- Inclusion criteria:
 - New State Fund claim: Identified by each state WC agency
 - At least one opioid prescription during the first 6 weeks after date of injury: Based on WC pharmacy billing data
 - Ability to speak English or Spanish (for the survey only): This will be determined by interviewers during the contact/consent process
- Exclusion criteria:
 - Under 18 years of age: Age at injury, calculated as the difference between birthdate and date of injury

Operational Definitions for Key Covariates

Operational definitions will need to be aligned as much as possible across the two states. Thus, key covariates and their operational definitions will need to be determined after (1) preliminary OH WC data are available for inspection and (2) the survey is finalized with stakeholder input.

Clustering

Study objectives and the primary and secondary outcomes for Aims 1 and 2/2A pertain to the individual worker level. Multiple outcome measures for each worker (both administrative and survey based) require accounting for within-person correlation, which motivates the use of GEE. However, provider-level opioid prescribing patterns may induce intraclass correlation among injured workers treated by a particular provider. Each ORP decision is specific to an individual patient; however, providers either request PA in WA or are notified of RR in OH. These experiences may cause providers to adjust their practice for other patients in their care, impacting outcomes for provider-based patient clusters. The vast majority of providers prescribe opioids to very few WC patients. However, there may be some dependence of patient observations within the few higher-volume providers. Injured workers may have multiple prescribing providers over the course of a WC claim, which complicates cluster identification.

The primary predictor for Aim 2A, COHE status, is assigned to injured workers based on provider-level COHE affiliation. COHE program features are determined at the WC system level but its effects may vary depending on provider adherence and individual worker circumstances. In order to obtain accurate standard errors and confidence intervals, we plan to specify models using robust standard error estimates and accounting for potential clustering by primary attending provider. This approach by necessity assumes person clusters are perfectly nested within attending provider clusters; however, attending provider can change over time. In practice such changes are uncommon in WA, and we are uncertain whether such changes can be tracked in OH. If feasible, we will assess clustering based on different approaches (e.g., first attending provider, attending provider in place for the longest period of time during the acute phase, or accounting for clustering only at the person level). We expect these approaches to yield similar results, but in the event they do not, we will proceed with the most conservative approach (highest standard errors).

Missing Data

Assumptions about the nature and prevalence of missing data made below will be assessed once preliminary WC and survey data sets are available. The administrative claims and pharmacy data are virtually 100% complete in WA; we will assess OH data when available, but expect similar completeness for all covariates associated with worker compensation or provider billing.

We expect relatively high survey response rates, based on previous research in these injured worker populations. Barriers to recruitment include being unable to locate and contact injured workers, and injured workers choosing to not participate. The address and phone numbers of injured workers who are receiving WC benefits are largely complete and accurate because contact information is required in order to receive disability benefits. In order to increase the response rate, all eligible workers identified by WA and OH WC systems will be sent an introductory letter 1 week prior to the initiation of the phone surveys. Workers will be able to schedule a time for the survey or can opt out at that point. Workers will be paid \$50 for the baseline survey, \$30 for the 6 month survey, and \$50 for the 12 month survey (\$130 total). The University of Washington (UW) Survey Research Division (SRD) will make 10 call attempts. The SRD research staff are extensively trained in standardized interviewing techniques and methods, effective calling strategies, building rapport and interest, and refusal prevention, which all aid in minimizing attrition and maximizing response rates. The survey interviewers are trained to minimize item non-response, while supporting autonomy not to answer individual questions.

Based on these efforts, we anticipate limited amounts of missing data for individual survey items, under 5%. We do expect larger and non-negligible amounts of missing 12-month outcome data relative to 6-month outcome data on the surveys, based on projected attrition.

We will use standard techniques to identify the nature (randomness) of missing data. Where missing data are minimal (<5%) and random (no clear associations with outcomes or predictors of interest), we will use casewise deletion; we expect this approach will be adequate for administrative data and baseline survey data. For the GEE panel models testing survey-based patient outcomes, we will use multiple imputation methods, based on an expected larger amount of missing data and the likely association of missingness with previous unsafe opioid prescribing.⁴

⁴ Aloisio, K. M., Swanson, S. A., Micali, N., Field, A., & Horton, N. J. (2014). Analysis of partially observed clustered data using generalized estimating equations and multiple imputation. *Stata J*, 14(4), 863-883.

We will examine predictors of survey non-response and loss-to-follow-up with descriptive statistics comparing the two groups (and potential differences by state), and potential differences will be noted when interpreting results from the analyses of survey data. Non-response adjustment using post-stratification weighting techniques will be implemented, if warranted due to differential non-response. We will record and report reasons for dropout and missing data, run sensitivity analyses if indicated, and account for all patients in reports.

8. Analytical Methods: Qualitative Analyses

Specific aim 3. Using qualitative methods, identify key environmental, programmatic and policy factors that influenced the design, implementation and impact of the PA program in WA and the RR program in OH. This information will lead to the development of an Opioid Review Tool educational module for dissemination to both public and private payers.

Aim 3 will provide important contextual information and insights to enable us to explain why the two states developed different strategies in designing and implementing their respective ORPs, and insight into ORP impact on providers and patients, beyond health outcomes.

Key Informants

During Year 2, we will conduct key informant interviews with policy makers and stakeholders who were involved in the creation and implementation of each state's ORP, including ORP reviewing pharmacists and nurses. Initial key informants in each state have already been identified; these are individuals, as available, who were important in the ORP design and implementation process (however, we will be unable to interview current and former BWC employees due to an ongoing lawsuit in OH). The remainder of the key informants will be identified through (a) snowball sampling, by asking each interviewed informant to name others involved in the policy-making process in their state, and (b) noting the identity of key players in ORP design and implementation mentioned in the policy documents we collect and explore. Each interview is likely to last 60-90 minutes. Key informants will be asked to share a range of information about the policy making process, including the origins of the ORP regulations about which they have expertise; considerations & alternatives explored; inputs to the policy-making process; how the specifics were designed and implemented; how necessary resources were obtained; push-back, setbacks, and decision-making milestones. Interviews will be digitally recorded and professionally transcribed. Once an initial picture of the policy development process has been obtained through key informants, policy documents that could provide additional details will be collected and analyzed. These documents may include reports, transcripts, testimony, position statements, policy drafts, and other materials produced by policy makers, issue stakeholders, executive agencies, and legislative hearings and committees.

Key informant interviews and policy document collection will be designed initially around Aim 3, but expanded to generate the data necessary to address Aim 1 as well. We will employ qualitative methods to understand the causes of unexplained fluctuations in the time series described in Analysis Topic A. Specifically, we will conduct targeted key informant interviews and analyze the specific policy documents most relevant to the time period immediately prior to any observed fluctuations. Interviews and document analyses necessary to complete Aim 1 will be timed to occur in tandem with the larger set of key informant interviews and policy documents necessary for Aim 3.

All qualitative data will be analyzed using a grounded theory approach, aided by Excel spreadsheets and NVivo qualitative data management software. These methods will focus on identifying causal factors that shaped state choices about which ORPs to design, how to implement them, and how these programs should evolve over time. Analytic methods will focus on inductive coding first, in order to facilitate identification of the broadest possible range of causal themes. Analysis will begin as soon as the first key informant interviews are complete; simultaneous data collection and analysis will allow later interviews to be informed by earlier ones, so that the fullest possible picture of policymaking can emerge.

Individual In-Depth Interviews

We will conduct 20 to 30 patient and around 10 provider interviews in each state. Interviewees will be identified from the lists provided to us by each state's WC agencies (and also through snowball sampling in the case of provider interviews). Participants will be recruited from among: (1) patients who had an opioid prescription for at least 6 weeks paid for by WC or whose prescription payments have been reviewed in accordance with the state's ORP, and (2) prescribing providers that had at least one patient whose opioid prescription paid for through WC had been reviewed in accordance with the state's ORP. Patient interviews will explore the impact of the ORPs and related policies on pain management, function, disability, return to work, their relationship with their provider, and their feelings about WC. Provider interviews will explore changes in their use of opioid prescriptions for injured workers, why they made these changes, and the role of ORPs and related policies on their prescribing changes; impact on feelings about clinical autonomy; views of the legitimate role of opioids in pain management; and reflections on consequences and effectiveness of the ORP, whether it should be changed, and whether the ORP affected their attitudes toward the state WC agency or their willingness to treat WC patients.

Interviews will be led by [name] and the qualitative research assistants in WA and OH. Each interview will last approximately 1-1.5-hours. Interviews will be audio-taped and professionally transcribed. Transcripts and notes will be analyzed using a grounded theory approach, aided by Excel spreadsheets and NVivo qualitative data management software.

9. Data Management Plan (DMP)

See Appendix A.

10. Data Safety Monitoring Plan (DSMP)

See Appendix B.

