Both prior authorization (PA) and other insurer-based drug utilization programs are increasingly being used in an attempt to stem the tide of the opioid epidemic and to reduce unsafe opioid prescribing. Review programs have proven effective in decreasing use and overall costs of more expensive medications. This study focuses on two states, Washington (WA) and Ohio (OH), which have witnessed the devastating consequences of the growing opioid crisis. WA was an early leader in state efforts to combat the opioid crisis; OH's efforts have come more recently. WA and OH offer a unique opportunity to study opioid prescribing interventions because both states have regulatory authority over health care delivery to all injured workers, and are the two largest states with a population-based exclusive State Fund. Further, both states have initiated distinct prescribing guideline-concordant opioid review programs (ORPs), allowing for a unique natural experiment to compare the effectiveness of two substantially different approaches to reducing unsafe opioid prescribing.

2. Research Objectives

Specific aim 1. Examine the comparative effectiveness of prospective prior authorization (PA) with hard stops in WA versus retrospective review (RR) with prescriber notification in OH in reducing unsafe opioid prescribing.

Hypothesis 1. Prospective PA with hard stops (WA) will be associated with statistically significantly less unsafe opioid prescribing compared to RR and prescriber notification (OH).

Specific aim 2. Examine the comparative effectiveness of WA's PA program versus OH's RR program with regard to patient reported outcomes (pain, function, quality of life, return to work), harms (presence of opioid use disorder, opioid poisoning events) and work disability outcomes at 6 weeks, 6 months, and 12 months from date of injury.

Hypothesis 2. Prospective PA with hard stops (WA) will be associated with statistically significantly improved patient outcomes compared to RR and prescriber notification (OH).

Specific aim 2A. For injured workers in WA, examine unsafe opioid prescribing and patient-reported

outcomes and work disability at 6 and 12 months for patients receiving an established, coordinated, stepped care management program during the first 12 weeks following injury plus prospective PA versus patients receiving usual care subject to PA only.

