Aim 3 patient in-depth interviews. Patients who had an opioid prescription for at least 6 weeks paid for by WC or whose prescription payments have been reviewed in accordance with the state's ORP.

Exclusion Criteria

Aims 1, 2, & 3 (patient in-depth interviews only). Injured workers who are under 18 years of age.

Aims 1 & 2. Current cancer diagnosis and (for surveys only) non-English or -Spanish speakers, physically or mentally incapable of completing the survey, incarcerated, or deceased.

Aim 3. Non-English speakers.

Number of Study Groups/Cohorts

The primary analysis involves 2 groups/cohorts of injured workers, 1 from WA and 1 from OH. Secondary analyses involve two subgroups of injured workers within WA, defined by whether the injured worker's attending provider participates in Centers of Occupational Health and Education (COHE) care delivery.

Enrollment/Sample Size

Aims 1 & 2. The time series for Aim 1 will be based on data for all injured workers in OH and WA who file a new State Fund claim from January 1, 2010 through December 31, 2020. For the prospective cohort analysis, we anticipate including 4,636 eligible workers in WA and 779 in OH for a one-year cohort. Using WC claims, pharmacy billing data, and potentially prescription drug monitoring program (PDMP) data from each state, we will track opioid prescribing for each injured worker for a full year after date of injury. The worker survey will largely be drawn from this cohort, depending on the length of time needed to conduct an adequate number of surveys. All workers will be interviewed initially at 4-6 weeks

after injury (baseline). Workers who complete the baseline survey in the first year of recruitment will be asked to complete follow-up surveys at 6- and 12-months after injury. Workers who complete the baseline survey after the first year of recruitment will be asked to *only* do the 6-month follow-up survey due to time constraints. We anticipate that roughly 3,120 workers in WA and 525 workers in OH will complete baseline surveys. We anticipate roughly 1,700 completed 12-month outcome surveys from WA and 234 from OH.

Aim 3 key informants. No more than 12 interviews in WA, supplemented with policy documents to add detail. In OH, we will start with policy documents and use key informant interviews with individuals outside of BWC to complement and supplement the historical account.

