Patient experience with opioid review procedures	Survey	Patient experience with opioid review procedures	6 months, 12 months
Perceived outcomes of insurer decisions from patient's perspective	Survey	Perceived outcomes of insurer decisions from patient's perspective	6 months, 12 months
Overall patient satisfaction	Survey	Overall patient satisfaction	6 weeks, 6 months, 12 months
Satisfaction with pain-related treatment	Survey	Satisfaction with pain-related treatment	6 weeks, 6 months, 12 months
Working full-time, part-time or not working	Survey	Working full-time, part-time or not working	6 weeks, 6 months, 12 months
Are wages more, less or about the same as before injury	Survey	Are wages more, less or about the same as before injury	6 weeks, 6 months, 12 months
Work status	WC claims data	Proxy: compensated time loss	6 weeks, 6 months, 12 months
Opioid poisoning events	WC billing data	ICD-10-CM codes	12 months

WC, workers' compensation.

Table 3. Exploratory/Other Outcome Measures

Title	Data Source	Description	Timeframe (after injury)
Opioid use disorder	Survey	TAPS (The Tobacco, Alcohol, Prescription medications, and other Substance Tool) – opiate pain reliever subset	12 months

7. Analytical Methods: Quantitative Analyses

Note: Because this is an observational study, and because we must submit this study protocol before Ohio data are made available, much of this plan is tentative. Updates will be made once more is known regarding the availability, completeness, and cross-state comparability of various data fields, data definitions, data generating processes, and procedures. A summary of the various planned analyses is provided in Table 4, followed by further detail regarding each analysis.

Table 4. Summary of Quantitative Data Analyses				
Aim	Analysis Topic	Analytic Approach	Outcome	Sample
1	A. Compare long-term prescribing patterns across states and identify discontinuities	Time series/ITSA	Any opioid prescription (acute) Unsafe opioid prescribing (subacute)	OH/WA 2010-2020
1	B. PA vs RR	GEE/propensity score & subgroup analysis	Unsafe opioid prescribing	OH/WA cohorts
1	C. PA vs RR	GEE/propensity score	Unsafe opioid prescribing	OH/WA survey samples
1	D. Prescribing data validation	Compare WC billing data with PDMP data	Unsafe opioid prescribing	OH/WA cohorts
1	E. Frequency/outcomes of opioid review decisions	Descriptives (N/percent that are/are not authorized)	Opioid review decisions	OH/WA cohorts

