Surveys will be conducted at approximately 6 weeks (baseline), 6 months, and 12 months after injury. We anticipate that roughly 3,120 workers in WA and 525 workers in OH will complete baseline surveys. Based on estimated response rates, we anticipate roughly 1,700 completed 12-month outcome surveys from WA and 234 from OH. Depending on survey eligibility and response rates, up to 100% of survey

respondents may be drawn from the underlying WA/OH cohorts (however, it is possible that survey accrual may need to continue beyond cohort accrual).

The primary predictor is binary (1 for WA cases, 0 for OH cases). We will specify GEE panel models as described for Analysis Topic B to account for outcome measures at multiple time points for each patient (6 months, 12 months). Appropriate GEE link functions will be specified for each outcome variable, e.g., identity link for continuous variables, logit link for binary variables, and log link for counts (Tables 2 and 3). Comparisons of clinically important improvements in patient pain and functioning will be based on the proportion of patients who achieve clinically meaningful improvement (relative to baseline) on our outcome measures at 6 and 12 months, as defined by 30% or greater improvement. We will include time/state interactions in order to assess (1) change in outcomes over time and (2) differences in such changes by state.

Covariates described under Analysis Topic B will also be included for this analysis, in addition to baseline covariates collected during the survey. Additional survey-based covariates will include the following (this list may be adjusted as the survey is finalized with stakeholder input):

- Education
- Household Income
- Race/ethnicity
- Health status
- Comorbidities (survey-based FCI, current cancer treatment)
- Pain intensity
- Physical function/pain interference
- Emotional functioning-Anxiety
- Emotional functioning-Mood
- Quality of life
- Work status and barriers to work
- Treatment for pain
- Satisfaction with treatment
- Communication with health care provider
- Alcohol and tobacco use

Using these covariates, we will calculate a propensity score. In order to minimize the loss of survey data, we plan to include this propensity score in the causal models along with important covariates. However, if needed to achieve balance on baseline variables, we will restrict the analytic sample to the region of common support and/or implement propensity score matching.

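### Opioid use disorder is measured only at 12 months with no baseline, so it cannot meet Aim 2's timing, fit the planned panel model, or separate new from pre-existing disorder.

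*Combined protocol and SAP*

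**What the plan says.** Section 2, Specific aim 2 (repeated in Section 7 under Aim 2) lists among its outcomes "harms (presence of opioid use disorder, opioid poisoning events) and work disability outcomes at 6 weeks, 6 months, and 12 months from date of injury".

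Section 6, Table 3 (exploratory/other outcomes) has one row, "Opioid use disorder". Its source is the survey, and its measure and timing are the TAPS "opiate pain reliever subset 12 months". The other harm, in Table 2, reads "Opioid poisoning events WC billing data ICD-10-CM codes 12 months". Pain, PHQ-4, EQ-5D-5L and satisfaction are scheduled at all three survey waves.

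Section 4, Enrollment/Sample Size puts the baseline interview at 4-6 weeks after injury. It adds that workers whose baseline survey falls after the first year of recruitment "will be asked to *only* do the 6-month follow-up survey due to time constraints".

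Section 7, Topic H covers secondary and exploratory outcomes and tests Hypothesis 2. It specifies GEE panel models "to account for outcome measures at multiple time points for each patient (6 months, 12 months"), with time/state interactions. Topic J applies the same analysis to COHE versus non-COHE care within WA.

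Section 7, Missing Data plans multiple imputation for survey outcomes, citing "the likely association of missingness with previous unsafe opioid prescribing".

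**The concern.** Aim 2 and Table 3 disagree on when opioid use disorder is measured, and the planned model needs repeated measurements that the schedule does not supply.

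The larger issue is the missing baseline. A 12-month measure of whether the disorder is present counts workers who already had it before either review program acted, together with those who developed it later. If the two states, or COHE and non-COHE patients, differ in pre-existing disorder, part of that difference carries into the comparison. At stake is whether Aim 2 can say anything comparative about this harm.

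**Working it through.** The documents give no rate, effect size or power for opioid use disorder, so there is no figure to reproduce. The check sets the sections side by side, then adds simple arithmetic.

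**1. Timing.** Aim 2 gives 6 weeks, 6 months and 12 months. Table 3 gives 12 months. Topic H states "Surveys will be conducted at approximately 6 weeks (baseline), 6 months, and 12 months after injury", so the two earlier waves exist but are not used for this outcome. Poisoning events have the same mismatch, but they come from billing data, where events can be dated.

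**2. Baseline information.** Topic H's survey covariates include pain, function, mood, health status, comorbidities, treatment for pain, and alcohol and tobacco use. They include no measure of opioid use disorder or misuse. Topic B's list adds opioid prescriptions in the 3 months before injury, only if monitoring-program data are available, and a prescription is not a measure of the disorder. Appendix A (Data collection) and Appendix B (Protection against risks) mention survey items on opioid use disorder and misuse without naming a wave, so they do not establish a baseline.

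**3. Was an earlier measurement possible?** The baseline interview is at 4-6 weeks. Under Section 5, WA denies payment for opioids billed beyond six weeks unless the checklist is submitted, and OH reviews records at 12 weeks. The interview precedes both.

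**4. Model.** With one wave there is no within-person repetition and no time term to interact with state. The panel and its interaction cannot be estimated.

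**5. Who is measured.** Inputs are from Enrollment/Sample Size and Topic H.
- WA: 1,700 / 3,120 = 54.5%
- OH: 234 / 525 = 44.6%

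The remainder (1,420 in WA and 291 in OH) combines lost respondents with late recruits never scheduled for 12 months. The documents do not split the two.

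**6. Effect of baseline imbalance (illustration; all rates assumed).** Let b be the pre-existing rate and i the rate of new disorder among the rest. Assume that pre-existing disorder persists, that detection is perfect and that response is complete. Then 12-month prevalence is p = b + (1 − b) × i, and OR = [p(WA)/(1 − p(WA))] / [p(OH)/(1 − p(OH))]. Setting i equal in both states means no program effect.

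Worked case: i = 2%, b = 2% in WA and 4% in OH.
- p(WA) = 0.02 + 0.98 × 0.02 = 3.96%
- p(OH) = 0.04 + 0.96 × 0.02 = 5.92%
- OR = (0.0396/0.9604) / (0.0592/0.9408) = 0.66

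| New disorder, i | Pre-existing WA / OH | p(WA) / p(OH) | OR |
|---|---|---|---|
| 2% | 2% / 2% | 3.96% / 3.96% | 1.00 |
| 2% | 2% / 4% | 3.96% / 5.92% | 0.66 |
| 2% | 2% / 6% | 3.96% / 7.88% | 0.48 |
| 2% | 4% / 2% | 5.92% / 3.96% | 1.53 |
| 4% | 2% / 2% | 5.92% / 5.92% | 1.00 |
| 4% | 2% / 4% | 5.92% / 7.84% | 0.74 |
| 4% | 2% / 6% | 5.92% / 9.76% | 0.58 |
| 4% | 4% / 2% | 7.84% / 5.92% | 1.35 |

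Even with balanced states and a 2% pre-existing rate, the pre-existing share of 12-month cases is 0.02/0.0396 = 51% (i = 2%) or 0.02/0.0592 = 34% (i = 4%). These odds ratios are before any covariate adjustment.

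**The case against.** The strongest reply is that this is one exploratory outcome, and that Aim 2 speaks of the presence of the disorder, which is prevalence. A reader might infer that the plan promises new-onset disorder; it does not. The closing time phrase in Aim 2 could also be read as attaching only to work disability, and the outcome tables set timing outcome by outcome: global improvement and disability, for example, are scheduled only at 6 and 12 months. Table 4 labels Topic H's outcomes as secondary, although the Topic H text also includes exploratory ones. All of this limits the severity. It does not supply a baseline or a model that fits, and Aim 2 still frames the outcome as comparative effectiveness, so pre-existing cases matter.

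Second, the plan has protections: a propensity score, baseline health and pain covariates, and conditional adjustment for prior prescriptions. A baseline difference would therefore not automatically be read as a program effect. This stands in part, because these are proxies and residual confounding remains possible.

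Third, a reader might infer that 12-month respondents are those least likely to show the harm. The Missing Data section states an association with previous unsafe prescribing but no direction for this outcome. It also plans comparison of responders and non-responders by state, post-stratification weighting if warranted and sensitivity analyses if indicated. Prescribing history can inform the imputation, although no earlier value of the outcome itself can.

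Fourth, the shares in step 5 might be taken for retention rates, or completers might be expressed as a share of the administrative cohorts. Neither is sound: late recruits are included in the baseline counts, and survey accrual may run beyond the cohort.

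Finally, a single-wave adjusted logistic comparison can be fitted. What cannot be fitted is the panel with its time interaction, and no alternative is specified.

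**Conclusion.** The point holds in a limited form. Three facts rest on the text alone: Aim 2's timing does not match Table 3; no baseline measure of the disorder is scheduled or listed as a covariate; and the Topic H and J panel with a time interaction does not fit an outcome seen once. Workers recruited after the first year are never measured.

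It follows that a state or COHE difference in pre-existing disorder could appear as a program difference, with only partial protection from the available covariates and propensity score. The illustrated range, odds ratios from 0.48 to 1.53 with no program effect, rests wholly on assumed rates. It shows that bias could run either way, not how large it is here. The documents do not support a claim that such bias has a known direction, or that it will occur. The outcome is exploratory, so the primary analysis is unaffected, but the comparative claim for this harm under Hypotheses 2 and 2A is not supported as planned.

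**What to change.** **Where surveys are still to be fielded:** ask the same TAPS opiate items at the 4-6 week baseline and at 6 months, amend Table 3, and adjust for the baseline value in Topics H and J. This costs a few more survey items. Such a baseline is before review, not before injury. For Topic J it falls inside the 12-week COHE period, and this limit should be stated.

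**If fielding is closed** (plausible, with a one-year cohort of injuries from July 2019 and a protocol dated November 2022): restate Aim 2 for this outcome as descriptive 12-month prevalence among respondents, remove it from the panel/interaction model and from the Hypothesis 2 and 2A tests, and state that new and pre-existing disorder cannot be separated. This costs wording only.

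**In either case:** state the wave of the survey items mentioned in Appendices A and B, align the timing of poisoning events in Aim 2 with Table 2, and report late recruits separately from attrition.

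**Optional supplement:** ICD-10-CM opioid use disorder diagnoses in workers' compensation billing for the full cohorts, reported beside the survey measure. This needs one more code list. Billing is likely to under-record the disorder, and detection may differ between a state using prescriber checklists and one using chart review. These diagnoses should not serve as a baseline or define new disorder, because a prior case first billed after week 6 would count as new.
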